1.0 Objectives

1.1 Study Objectives

Blind procedures are basic to the practice of obstetrics and gynecology and often require substantial experience to master. Ultrasound is increasingly used to guide uterine procedures that have traditionally been performed blindly such as embryo transfer. Currently there are limited prospective trials for studying the utility of ultrasound guidance for many other procedures. Our objective is to determine the utility of ultrasound-guided intrauterine device (IUD) insertion compared to traditional blind insertion at an academic health institute where skill level of provider can vary greatly. The subject and her clinician will determine which type of IUD they will receive and all types of IUD's (copper and progesterone containing) will be acceptable for participation in the study. Our hypothesis is that transabdominal ultrasound guided insertion will lead to lower discontinuation rates and greater patient satisfaction.

1.2 Primary Study Endpoints

IUD discontinuation rate at 6 months

1.3 Secondary Study Endpoints

Malposition rate at the time of 4-6 week post insertion string check
Pain during insertion as determined by the visual analog scale (VAS)
Satisfaction at 6 months determined by categorical assessment and rate of side effects as reported by patient

2.0 Background

2.1 Scientific Background and Gaps

Blind procedures are basic to the practice of obstetrics and gynecology, but often require substantial experience to master. Ultrasound is increasingly used to guide uterine procedures that traditionally have been performed blindly such as embryo transfer. Currently, there is one small randomized trial that studied malposition rates 1 week following IUD insertion with ultrasound guidance compared to blind insertion and found promising data to support use of US guidance [1]. However, that trial is limited in its small sample size of 40 per arm and short follow up of 1 week. There still is paucity of information on the effect of ultrasound guidance on long term discontinuation rate, complications, and satisfaction compared to blind insertion.

2.2 Previous Data

There are no preliminary data at this time

2.3 Study Rationale

Our goal is to determine the utility of ultrasound guided IUD insertion compared to the traditional blind insertion at an academic health institute where the skill level of the provider can vary greatly. We hypothesize that ultrasound-guided insertion will lead lower IUD discontinuation rates and greater patient satisfaction.

3.0 Inclusion and Exclusion Criteria

3.1 Inclusion Criteria

1. Female >18 years of age undergoing IUD insertion in an office setting
2. Fluent in spoken and written English
3. Premenopausal

3.2 Exclusion Criteria

1. Less than 6weeks postpartum at time of IUD insertion
2. Intraoperative IUD insertion
3. Pregnant
4. Prisoners
5. Cognitive impairment
6. unable to read or write

3.3 Early Withdrawal of Subjects

3.3.1 Criteria for removal from study

- Subject withdraws consent
- A decision by the investigator to withdraw subject due to safety reasons

3.3.2 Follow-up for withdrawn subjects

Subjects who withdraw prior to IUD insertion will not receive the intervention and will not receive any research related follow up, they will receive routine follow up as directed by their physician.

Subjects who withdraw after the IUD insertion will still receive their routine care 4-6 week string check follow up but will not have the concomitant research ultrasound to check positioning of IUD.

Those who withdraw after IUD insertion will also not have a 6-month clinic follow up visit for string check and satisfaction Likert scale completion.

4.0 Recruitment Methods

4.1 Identification of subjects

Participants will be identified in several ways:

- By the PI/SI during a patient clinic visit
 - The study team may also review the investigator's and coinvestigator's clinic schedules for patients who are scheduled for an IUD insertion. If subjects are not identified during a clinic visit and given the information they will be contacted by the study coordinator to see if they are interested and the study coordinator will explain the study and send them the consent form to review before their IUD insertion appointment. If the study coordinator is unable to reach the subjects, a letter from the PI and a copy of the ICF will be mailed to the patient's

home address. The letter provides contact information for the study coordinator and co-PI so the patient can call or email with any questions prior to their appointment.

4.2 Recruitment process

Women will be given information on the study at the time of scheduling for the IUD insertion clinic appointment, either in the clinic appointment when she is considering IUD or inpatient for those considering an IUD postpartum (greater than 6 weeks after delivery). Eligibility will be determined by the investigator and women who are eligible will be given information about the study by the investigator. They will have the opportunity to ask questions and if they are interested in participating they will be given a copy of the consent form to take home and read. Upon arrival in clinic for IUD insertion, if the subject is interested in participating, they will again be counseled about the study and will be given time to ask questions and have their questions answered. If they are eligible to continue, informed consent will be obtained, and they will be randomized to one of the two treatment arms, traditional IUD insertion versus transabdominal ultrasound-guided insertion.

4.3 Recruitment materials

None

4.4 Eligibility/screening of subjects

Not applicable

5.0 Consent Process and Documentation

5.1 Consent Process

5.1.1 Obtaining Informed Consent

5.1.1.1 Timing and Location of Consent

Subjects will be consented at their clinic visit prior to undergoing their IUD insertion. The subject will have been given the consent form at their previous visit or while inpatient to read at home. We will again discuss the study and answer any and all questions the patient may have. At this appointment, the patient will sign the consent form if they agree to continue in the study.

5.1.1.2 Coercion or Undue Influence during Consent

All subjects will be informed at their visit that their participation in the study is entirely voluntary and they will continue to receive routine care whether they consent or decide not to consent to the study.

5.1.2 Waiver or alteration of the informed consent requirement

A waiver of consent is requested to review medical record information to determine preliminary eligibility to participate in the research

5.2 Consent Documentation

5.2.1 Written Documentation of Consent

The consent process will be documented in writing with the long form of consent documentation at the IUD insertion clinic visit:

- The current IRB approved consent form will be obtained.
- We will verify that we are using the most current IRB-approved version of the study specific consent form and that the consent form is in language understandable to the subject.
- A copy of the consent form will be provided to the subject. Whenever possible the consent form will be provided to the subject in advance of the consent discussion.
- .

5.2.2 Waiver of Documentation of Consent (Implied consent, Verbal consent, etc.)

Not applicable

5.3 Consent – Other Considerations

5.3.1 Non-English Speaking Subjects

Not applicable

5.3.2 Cognitively Impaired Adults

5.3.2.1 Capability of Providing Consent

Not applicable

5.3.2.2 Adults Unable To Consent

Not applicable

5.3.2.3 Assent of Adults Unable to Consent

Not applicable

5.3.3 Subjects who are not yet adults (infants, children, teenagers)

5.3.3.1 Parental Permission

Not applicable

5.3.3.2 Assent of subjects who are not yet adults

Not applicable

6.0 HIPAA Research Authorization and/or Waiver or Alteration of Authorization

6.1 Authorization and/or Waiver or Alteration of Authorization for the Uses and Disclosures of PHI

Check all that apply:

- Not applicable, no identifiable protected health information (PHI) is accessed, used or disclosed in this study.** *[Mark all parts of sections 6.2 and 6.3 as not applicable]*
- Authorization will be obtained and documented as part of the consent process.** *[If this is the only box checked, mark sections 6.2 and 6.3 as not applicable]*
- Partial waiver is requested for recruitment purposes only (Check this box if patients' medical records will be accessed to determine eligibility before consent/authorization has been obtained).** *[Complete all parts of sections 6.2 and 6.3]*
- Full waiver is requested for entire research study (e.g., medical record review studies).** *[Complete all parts of sections 6.2 and 6.3]*
- Alteration is requested to waive requirement for written documentation of authorization (verbal authorization will be obtained).** *[Complete all parts of sections 6.2 and 6.3]*

6.2 Waiver or Alteration of Authorization for the Uses and Disclosures of PHI

6.2.1 Access, use or disclosure of PHI representing no more than a minimal risk to the privacy of the individual

6.2.1.1 Plan to protect PHI from improper use or disclosure

Information is included in the Research Data Plan Form.

6.2.1.2 Plan to destroy identifiers or a justification for retaining identifiers

Study information will be destroyed after the research has ended and all institutional/regulatory requirements for data retention have been met

6.2.2 Explanation for why the research could not practicably be conducted without access to and use of PHI

Information must be obtained from the subject's electronic medical record during recruitment to determine eligibility and, in some cases, to confirm information discussed with the subject in regards to their medical history.

6.2.3 Explanation for why the research could not practicably be conducted without the waiver or alteration of authorization

The waiver is requested only for recruitment to determine subject eligibility to ensure that no medical conditions that fall into the exclusion criteria are present and would thus preclude enrollment. This waiver will minimize the enrollment of subjects' who may ultimately fail to meet the study inclusion/exclusion criteria.

6.3 Waiver or alteration of authorization statements of agreement

Protected health information obtained as part of this research will not be reused or disclosed to any other person or entity, except as required by law, for authorized oversight of the research study, or for other permitted uses and disclosures according to federal regulations.

The research team will collect only information essential to the study and in accord with the ‘Minimum Necessary’ standard (information reasonably necessary to accomplish the objectives of the research) per federal regulations.

Access to the information will be limited, to the greatest extent possible, within the research team. All disclosures or releases of identifiable information granted under this waiver will be accounted for and documented.

7.0 Study Design and Procedures

7.1 Study Design

Prospective, randomized trial.

7.2 Study Procedures

Table of visits:	Visit 1 Routine Visit	Visit 2 IUD Insertion Visit	Visit 3 Routine 4-6 Week String Check and transvaginal US	Visit 4 6 Month Clinic String Check or Phone Contact
Confirm Inclusion/Exclusion Criteria	X ^a	X ^a		
Complete Demographic form		x		
Consent		X ^a		
Randomization		X ^a		
Complete Visual Analogue Score before and after procedure(VAS)		X ^a	X ^a	X ^a
String check			X ^c	X ^a
Transvaginal US			X ^b	X ^a
Transabdominal US		X ^a		
Adverse Events		X ^a	X ^a	X ^a
Likert Scale			X ^a	X ^a

X^a - indicates research related events

X^b – indicates both research and standard of care events

X^c – indicates routine, standard of care

7.2.1 Visit 1-Pre-Insertion Visit:

All interested women undergoing a scheduled IUD insertion will be screened for inclusion/exclusion criteria by the study coordinator or investigator prior to their clinic visit. Those who meet the inclusion/exclusion will be offered information about the study during their clinic visit. The subject will have the study explained to them in detail by the investigator conducting the clinic visit and will be given ample time to have their questions answered. The subject will be given a copy of the consent form to take home and read prior to their IUD insertion visit. The subject will be given information on how to contact the investigator if she has any questions.

7.2.2 Visit 2 (Consent and IUD insertion)

Consent will be obtained from subjects at their IUD insertion visit. The investigator will again review the study with the patient and any questions the patient has about the study will be addressed. After all questions are answered to the patient's satisfaction written consent will be obtained. Demographic information will be collected from each subject.

Subjects will then be randomized to one of two groups:

Group A: traditional blind IUD insertion.

Group B: transabdominal ultrasound guided IUD insertion.

Subjects will be randomized to either US guided or traditional placement of IUD using 1:1 allocation. The randomization scheme for this study will use variable-size, random permuted blocks to ensure that the number of participants in each treatment arm is balanced after each set of B randomized participants, where B is the block size. After meeting eligibility criteria and being consented for the study, a subject will be ready to be randomized. Team members that have REDCap access will access REDCap to carry out the randomization assignment. If no team member is available with REDCap access the Co-PI ([name]) will be contacted and will enter the relevant subject information into REDCap and REDCap will return a randomization assignment. The randomization will then be relayed to the study team member to carry out the assigned randomization. If REDCap is offline and unavailable at the time of randomization, or [name] is not able to be contacted, [name] at Penn State Hershey Medical Center will have randomization assignments on paper as a backup hardcopy in order to randomize a patient. Subject in both groups will fill out a visual analogue score (VAS) before and after the procedure grading their pain.

Subjects will be instructed to call the investigator if they experience any abnormal uterine bleeding or problems with their IUD.

7.2.3 Visit 3 (4-6 weeks after Visit 2) Subjects will be scheduled to return to REI clinic 4-6 weeks after insertion of the IUD as routine follow-up. Subjects will be asked about any adverse events. Subjects will be asked to complete the Likert scale to indicate their satisfaction level with their IUD and the Visual Analogue Scale to indicate their level of pain. A routine string check in the form of a speculum exam will be performed in addition to a transvaginal ultrasound to confirm positioning of the IUD. If malposition is determined, then routine care will be to remove the IUD. The ultrasound operator will be blinded to the subject's arm in the study

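### Provider skill varies, so must the protocol fix and record who inserts the IUD before the arm is released?

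*Combined protocol and SAP*

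**What the plan says.** Section 1.1 sets the comparison "at an academic health institute where skill level of provider can vary greatly", and section 2.3 repeats the point: "at an academic health institute where the skill level of the provider can vary greatly". Section 16.4 allows care by a physician or a licensed nurse practitioner. Section 16.5 says the physician investigators have been trained in IUD insertion and do it routinely. It gives no experience threshold and does not speak of nurse practitioners.

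On allocation, section 7.2.2 says: "After meeting eligibility criteria and being consented for the study, a subject will be ready to be randomized". On the ordinary route, a team member with REDCap access obtains the assignment directly. Only if no such person is available is the Co-PI contacted, who "will enter the relevant subject information into REDCap and REDCap will return a randomization assignment". On that route, "The randomization will then be relayed to the study team member to carry out the assigned randomization".

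The Visit 2 column of the table in section 7.2 has a "Complete Demographic form" row and rows for consent, randomisation, VAS, transabdominal ultrasound and adverse events. It has no row for the inserter. Section 8.3 specifies an intention-to-treat comparison by modified Poisson regression, with age as an example of an adjustment variable. Section 9.0 refers data management to a separate form that is not part of the documents.

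**The concern.** The procedure depends on the operator, and the operator cannot be blinded. Randomisation balances what is settled before allocation; it does not protect a choice made afterwards. If a more experienced clinician tended to take over in one arm once the assignment was known, part of any difference in discontinuation would reflect who inserted the IUD and not the ultrasound guidance. Switching in the other direction could hide a real effect.

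The protocol itself says that skill varies widely, so a reader of the results may well ask whether operators were comparable between arms. No section specifies a record for each insertion of the intended and the actual inserter, which is what a full answer would need.

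**Working it through.** **The plan's own figure.** Section 8.2 assumes 23% against 11.5%, two-sided 5%, 80% power. With pooled proportion (0.23 + 0.115)/2 = 0.1725:

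n = [1.960·√(2·0.1725·0.8275) + 0.842·√(0.23·0.77 + 0.115·0.885)]² / 0.115² = 168.2, so 169 per group and 338 in all. Then 338/0.9 = 375.6, so 376. The stated numbers reproduce and are not in dispute.

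**Assumptions for the bias.** The documents give no discontinuation rate by experience and no share of insertions by experience. Two gaps are assumed: 33% (less experienced) against 23% (experienced), the closer to section 8.2, which bases its 23% on experienced clinicians; and a wider 35% against 18%. The rate in an arm is share × less-experienced rate + (1 − share) × experienced rate.

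**False-positive rate with no true effect.** Exact binomial enumeration, 169 per arm; the two values are the Wald test on the log risk ratio and the pooled z test.

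| Gap | Less-experienced share, blind v guided | Rates | Risk ratio | Rejection |
|---|---|---|---|---|
| 33% v 23% | 30% v 20% | 0.260 v 0.250 | 0.96 | 5.3%, 5.5% |
| 33% v 23% | 40% v 10% | 0.270 v 0.240 | 0.89 | 9.4%, 9.7% |
| 35% v 18% | 30% v 20% | 0.231 v 0.214 | 0.93 | 6.3%, 6.7% |
| 35% v 18% | 40% v 10% | 0.248 v 0.197 | 0.79 | 19.6%, 20.5% |
| 35% v 18% | 30% v 30% | 0.231 v 0.231 | 1.00 | 4.7%, 5.1% |

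For example, the first row is 0.3 × 0.33 + 0.7 × 0.23 = 0.260 and 0.2 × 0.33 + 0.8 × 0.23 = 0.250.

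**How much switching this takes.** The 30% v 20% rows need 0.10 × 169 ≈ 17 guided insertions moved. The 40% v 10% rows, from a common 25%, need 0.15 × 169 ≈ 25 in each arm and in opposite directions: about 50 of 338, or 15%.

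**Loss of power.** With a true risk ratio of 0.5, the wider gap, and shares of 20% (blind) v 30% (guided), the rates are 0.214 and 0.231 × 0.5 = 0.1155. Power is 68–69%, against 77% with 20% in both arms (0.214 v 0.107) and 80–81% with 30% in both (0.231 v 0.1155).

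**A second set of assumptions.** Half of insertions by skilled hands, 23% overall, skilled-to-less-skilled risk ratio 0.5 to 0.8, normal approximation. A 20-point difference in skilled share gives 10.3% down to 5.6% false positives. A 50-point difference gives 38.7% down to 8.6%, but needs 0.25 × 169 ≈ 42 switches in each arm.

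**What a pre-allocation field would do.** With the wider gap, adjusting for the level declared before allocation gives risk ratios of 0.926 (30% v 20%) and 0.794 (40% v 10%), the same as unadjusted. The declared level is balanced by design, so it carries no information about later switching. It explains 0.3·0.7·0.10²/(0.26·0.74) = 1.1% of outcome variance with the narrower gap and 0.3·0.7·0.17²/(0.231·0.769) = 3.4% with the wider one, so stratifying or adjusting gains little precision.

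**The case for a change.** The best case for a change is that the trial is about guidance where skill differs, the operator knows the arm, and the intended inserter cannot be reliably reconstructed later. One field before allocation and one for the actual inserter would cost almost nothing and would leave the sample size and primary model alone. Much of this stands. No section ties a named inserter to a woman before her arm is known. Section 16.5's training statement narrows the likely skill gap without closing it, and the delegation log is kept by study role and not by insertion.

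Several points reduce its force. Section 4.1 finds women through the investigators' "clinic schedules for patients who are scheduled for an IUD insertion", so a booked clinician usually exists before allocation. Setting that booking against the clinical record, where it names the inserter, could give a partial check, though an imperfect one if the schedule holder is not the person who inserts. Section 4.2 places the final discussion at the insertion visit itself: "Upon arrival in clinic for IUD insertion, if the subject is interested in participating, they will again be counseled about the study". That leaves a short interval for rearranging staff. The relay wording in section 7.2.2 belongs to the fallback route, where a team member is already with the patient; it is weak evidence that the inserter is left open. Finally, a field of this kind would normally be specified in the REDCap forms or the data plan form, which are not among the documents.

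**Conclusion.** No change to the plan is needed. This is missing operational detail, not a rule that gives a wrong result: nothing in the protocol directs or describes a change of inserter after allocation. In the assumed case nearest to section 8.2, with modest switching, the false-positive rate stays at 5.3–5.5%. Material inflation appears only with large arm-dependent switching, a wide assumed skill gap, or both, and the documents support neither. All of these sizes rest on assumed gaps and shares, so they show what would be required and do not estimate what will occur.

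The proposed field records an intention. It does not stop a switch, adjusting for it does not correct one, and the intention-to-treat analysis would be the same with or without it. What it would add is a descriptive table of inserters by arm. The study team may sensibly collect this on its forms, and may already do so, but the design and primary analysis do not depend on it.

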7.2.4 Visit 4 (Clinic visit or phone Visit-6 months after IUD insertion)

At 6 months subjects will be scheduled to return to REI clinic to have an IUD string check and if no strings are visualized then this will be categorized as malposition and the investigator will continue with routine care and work up Subjects who return to clinic for Visit 4 will also have a transvaginal ultrasound performed.

If the subject does not present for a clinic follow up, then she will be contacted by the Study Coordinator or investigator via phone to see if they still have their IUD in place (and when it was removed or lost).

All subjects will be surveyed for pain with the VAS and any adverse events (including abnormal uterine bleeding) will be recorded. All subjects will be asked to categorically rate their satisfaction with the IUD on a Likert Scale.

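### Does the lack of a written definition of IUD discontinuation leave the primary count open?

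*Combined protocol and SAP*

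**What the plan says.** Section 1.2 states the primary endpoint in full as "IUD discontinuation rate at 6 months". Section 8.3 adds the model (modified Poisson regression, intention to treat) but no event definition.

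The sections that generate or record events are these:

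- **Section 7.2.3 (Visit 3, 4-6 weeks):** string check and transvaginal scan for women in both arms, with the scan operator blinded to arm. "If malposition is determined, then routine care will be to remove the IUD".
- **Section 1.3:** the secondary endpoint is "Malposition rate at the time of 4-6 week post insertion string check", so it is tied to Visit 3 only.
- **Section 7.2.4 (Visit 4, clinic):** "if no strings are visualized then this will be categorized as malposition", followed by usual work-up. Also, "Subjects who return to clinic for Visit 4 will also have a transvaginal ultrasound performed".
- **Section 7.2.4 (Visit 4, phone):** women who do not attend are called "to see if they still have their IUD in place (and when it was removed or lost").
- **Section 8.3 (secondary analysis):** time runs from insertion to discontinuation, and a woman whose device has not come out by 6 months is censored there.

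The Visit 3 scan is described in two ways. Section 3.3.2 says withdrawn women will have the string check "but will not have the concomitant research ultrasound to check positioning of IUD", while the key to the table in section 7.2 gives that scan the mark that "indicates both research and standard of care events".

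**The concern.** Three kinds of event are not settled by the endpoint wording.

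1. **Replacement.** A woman whose malpositioned device is removed at Visit 3 and replaced could be counted as discontinued (the first device came out) or continuing (she still uses an IUD). Asked by phone whether she still has her IUD, she could say yes.
2. **Missing strings at Visit 4.** These are labelled malposition, but an expelled device also shows no strings and would be recorded as lost if reported by phone. The Visit 4 label belongs to no listed endpoint.
3. **Removal prompted by the Visit 4 check.** Only clinic attenders have the check and scan, and no visit window says on which side of 6 months a resulting removal falls.

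Malposition removals are also where the arms are most expected to differ, since section 8.2 attributes the projected halving of discontinuation to better placement. With an efficacy look planned near the midpoint and no DSMB, the fear is that the counting rule could be chosen once arm results are known, and that the choice could decide the primary test.

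**Working it through.** **Step 1. Reproduce the plan's sample size.** Inputs from section 8.2: 0.23 vs 0.115, two-sided 0.05, 80% power, 10% dropout. With pooled variance and mean rate 0.1725:

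n = [1.960·√(2·0.1725·0.8275) + 0.842·√(0.23·0.77 + 0.115·0.885)]² / 0.115² ≈ 168.3, so 169 per arm and 338 in total. Then 338/0.9 = 375.6, so 376. The plan's figures reproduce.

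**Step 2. Result at the design rates.** 0.23 × 169 = 38.9, about 39 blind-arm events; 0.115 × 169 = 19.4, about 19 guided-arm events. For the unadjusted modified Poisson model, with a and b the event counts and n the arm size, SE(log RR) = √(1/a − 1/n + 1/b − 1/n). Here it is √(1/39 + 1/19 − 2/169) = 0.258. RR = 19/39 = 0.49 (95% CI 0.29 to 0.81), p = 0.005.

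**Step 3. Reclassify events until p reaches 0.05.**

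| Change (169 per arm) | Blind vs guided | RR | p |
|---|---|---|---|
| 6 blind-arm events removed | 33 vs 19 | 0.58 | 0.038 |
| 7 removed | 32 vs 19 | 0.59 (0.351 to 1.005) | 0.052 |
| 8 removed | 31 vs 19 | 0.61 (0.36 to 1.04) | 0.070 |
| 9 blind and 1 guided removed | 30 vs 18 | 0.60 | 0.066 |
| 12 blind and 4 guided removed | 27 vs 15 | 0.56 | 0.052 |
| 6 guided-arm events added | 39 vs 25 | 0.64 | 0.055 |
| 48% removed from each arm (about 19 + 9) | 20.3 vs 9.9 | 0.49 | 0.053 |

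With a pooled chi-square test, 8 blind-arm removals are needed rather than 7 (p = 0.048 at 7, 0.066 at 8). At 188 per arm (43 vs 22) the modified Poisson figure is 8 (p = 0.065). Across rounding, arm size and test, the single-arm range is about 5 to 9. Adding equal numbers to both arms, up to 99 each, never crossed 0.05. The 0.05 threshold ignores any alpha spent at the interim look.

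Seven women are 7/169 = 4.1% of the blind arm. To move under a woman-level count, each must have had her device removed, had it replaced and kept the replacement to 6 months. The documents give no rate for malposition, replacement or missing strings, so the chance of reaching 7 cannot be computed.

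**Step 4. Apply the existing wording to each case.**

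- *Replacement.* Section 8.3 starts the clock at insertion and asks whether that device is still there at 6 months. Its time-to-event outcome is the same discontinuation as in the primary analysis. Removal ends the course of that device whatever follows. A Visit 3 removal follows a finding at a study visit, and the phone contact asks for the date a device was removed or lost, so the count need not rest on a later yes or no.
- *Missing strings.* These women are in clinic, have a transvaginal scan at the same visit and go on to work-up. That can help separate an absent device (discontinued) from a retained one (in place). The Visit 4 label enters no listed endpoint, so it changes no planned result.
- *Visit 4 removal.* A device found in place at the 6-month visit was in place at 6 months; a removal prompted by that check comes afterwards. Phone contacts can be placed against the 6-month mark by removal date.

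**The case for a change.** The strongest case for a change is that the primary event should be defined outright, not inferred from the censoring rule of a secondary analysis. Replacement is nowhere mentioned, one paragraph would settle it, and the events at issue lie on the pathway the trial is testing. With an interim efficacy look, no DSMB and blinding stated only for the Visit 3 scan operator, nothing formally prevents the rule from being fixed late.

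Part of this stands. The definition is implicit, and the arithmetic is correct for the scenario it models.

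The rest is weaker. The 7-to-8 figure covers one path only: net moves out of the blind arm from discontinued to continuing, at exact design rates. Counting missing strings as discontinuation would work the other way, by adding events. The alternative count, whether the woman uses any IUD at 6 months, answers a different question from survival of the inserted device, so it is not a rival reading of the same endpoint. Late choice of a rule is conjecture drawn from the interim and oversight arrangements, which are separate matters. Device identity and reason for removal may be on the case report form, which is not among the documents.

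The two descriptions of the Visit 3 scan do differ and should be reconciled, but the label does not enter the primary count. Overlap between the primary endpoint and the secondary malposition endpoint is not an error.

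**Conclusion.** No change to the plan follows. The gap is one of missing detail that an analyst would fill from the plan's own wording: follow the device inserted at Visit 2; count its removal or expulsion before the 6-month assessment, with or without replacement; and treat a device found in place at that assessment as continuing. No stated rule produces a wrong primary result. The Visit 3 scan is scheduled alike in both arms with a blinded operator, and the Visit 4 malposition label feeds no listed endpoint.

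On size: at exact design rates, a net shift of 7 to 8 blind-arm women (about 5 to 9 across single-arm variants), or about 28 events if both arms lose the same share, would be needed to lose significance. This rests on the assumed 23% and 11.5%, the unadjusted test at 0.05, and a departure from the natural reading of section 8.3. How many such events would occur cannot be derived from the documents. Extra form items, a woman-level sensitivity analysis and a table of removals by reason would add description but would not correct the planned comparison.
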